### Taking Care of Us Intervention

*Taking Care of Us* is a theoretically and empirically informed intervention that is communication-based and relationship-focused, building on the strengths of the dyad while fostering new skills. Briefly, the Theory of Dyadic Illness Management focuses on the care dyad as an interdependent unit. The theory proposes that dyads who have shared illness appraisals, and collaborate and communicate to manage the illness have better health outcomes at the dyadic and individual level. The proposed intervention is directly informed by this theory by a) targeting the dyad as the focus of the intervention rather than the individual patient or care partner, b) integrating the needs of both members of the dyad to move towards shared goals of care, and c) targeting the main concepts of the theory dyadic appraisal, dyadic collaboration and communication to manage illness - as the processes that optimize dyadic and individual health. Measures of both dyadic and individual health are included.

Control Group: Dyads randomly assigned to the attention-control group (SUPPORT) will receive three educational sessions **at 0, 4 and 8 weeks** guided by the Heart Failure Society of America (HFSA) education

modules (<https://hfsa.org/heart-failure-educational-modules>). The first session will be identical to session 1 in the TCU program regarding a general overview of the importance of HF symptom management per the HFSA modules. The two subsequent sessions for the control condition will focus on healthy eating and physical activity.

Survey data will be gathered from both patients and their spouse care partners for the explicit purpose of research. Patient and spouse surveys will include demographic and background questions and measures of patient and care partner quality of life, depressive symptoms, anxiety, healthcare utilization, engagement in HF management behaviors, confidence to manage HF, communication, perceptions of relationship quality, social support and the impact of Coronavirus on several aspects of their life. In addition, both patients and care partners will be asked to appraise the patient's dyspnea, pain interference and fatigue. Finally, patients will be asked to rate their HF-related QOL and spouses will be asked to rate their care-related strain. Patients and care partners will be asked to respond to questions about the strengths and weaknesses of the program they participated in at both **two months** and **five months** assessment (see attachment).

#### Measures Relevant to Aim 1 (Dyadic & Individual Health)

General health: The 10-item PROMIS Global Health short form will be used as a general measure of QOL for patients and care partners. The measure includes specific ratings of physical, mental and overall QOL.

Depressive symptoms: The Center for Epidemiological Studies-Depression (CES-D) scale is a widely used measure of depressive symptoms. Participants respond to 20 statements (based on feelings during the past week) using the response categories 1=rarely or none, 2=some or a little, 3=occasionally or moderate, and 4=most or all. The potential range of scores is 0-60, with higher scores indicating greater depressive symptomatology. The CES-D scale has been widely used with older adults, demonstrating good internal consistency with Cronbach's alpha in the .86 to .92 range in samples of FMs and cancer PTs. Sensitivity, specificity and validity of the scale have also been supported. Anxiety: Patient and care partner anxiety will be measured using the 4-item PROMIS Anxiety short form.

Healthcare Utilization: The Stanford Patient Education Research Center (PERC) Healthcare Utilization assessment will be used at 0 and 28 weeks to collect physician, mental health, emergency room visits and hospitalizations for both patients and care partners. Care-related strain: The Multidimensional Caregiver Strain Index (MCSI) will be used to capture physical, social and interpersonal strain, time constraints and demands.

HF-Specific QOL: The Kansas City Cardiomyopathy Questionnaire (KCCQ), a 12-item Likert scale will be used to measure patient HF-specific quality-of-life. Scores range from 0-100 with higher scores reflecting better QOL. Cronbach's alpha on these subscales range from 0.75-0.85.

#### Measures Relevant to Aim 2 (Dyadic Symptom Appraisal & Dyadic Management)

Patient and care partner appraisal of the patient's symptoms will be measured at all waves using measures from our previous HF and dyadic appraisal research. Dyspnea will be measured with the 6-item dyspnea subscale of the Heart Failure Somatic Perception Scale (HFSPS Dyspnea). The HFSPS asks about how much the patient was bothered by dyspnea during the last week on a 0 (not at all) to 5 (extremely bothersome) scale. The measure has demonstrated strong reliability and validity. Pain Interference will be measured using the psychometrically sound 6-item PROMIS pain interference scale. Fatigue will be measured using the 8-item PROMIS fatigue scale. HF Management Behaviors: Patient and care partner engagement in HF management will be measured using the management scores of the Self-Care of HF Index v6.2 (SCHFI). The SCHFI has 6 items that capture HF management. Response options range from 1 (not likely) to 4 (very likely). Scores are standardized to 0-100 with higher scores indicating greater engagement. The scale has demonstrated good reliability and validity across HF populations and care partners (CC-SCHFI), including our recent studies. In addition, patients and care partners will be asked to rate how much they collaborate regarding HF management behaviors using modified versions of the measure. Dyadic Heart Failure Management:

Collaborative management around heart failure will be measured using the revised Stanford Chronic Disease Self-Management measure. Patients and spouses are asked to rate their level of collaboration around six aspects of the patient's heart failure (e.g., fatigue, emotional distress) on a 0 (never) to 10 (always) scale. A summary score is created by calculating the mean collaboration level across the six items. Self-Efficacy to

Manage HF: Patients and care partners will be asked to rate their self-efficacy to manage heart failure using the Stanford Chronic Disease Self-Management measure. Patients and spouses are asked to rate their self-efficacy to manage six aspects of the patient's heart failure (e.g., fatigue, emotional distress) on a 0 (no confidence) to 10 (totally confident) scale. A summary score is created by calculating the mean self-efficacy level across the six items. Finally, the 5-item common/joint dyadic coping subscale from the Dyadic Coping Inventory will be used to measure how much couples engage in collaborative coping. Patients and spouses respond to each item (e.g., joint problem-solving, communication) on a 1 (very rarely) to 5 (very often) scale. The scale has demonstrated strong reliability and validity across contexts and cultures. Dyadic

Communication: Two aspects of Dyadic Communication/Coping will be measured. The Dyadic Coping measure consists of two subscales (active engagement and protective buffering). Active engagement assesses the extent to which the patient and spouse view their partner's active involvement and support. Participants respond to five items using a Likert scale from 1 (never) to 5 (very often). Higher scores indicate higher levels of perceived active engagement. The scale has exhibited high Cronbach's alpha values (.77 to .97) in studies of couples with cancer. Protective buffering assesses the extent to which the patient and spouse view their partner's use of hiding concerns and denying worries. Participants respond to six items using a Likert scale from 1 (never) to 5 (very often). Higher scores indicate higher levels of perceived protective buffering. The scale has exhibited high Cronbach's alpha values (.75 to .87) in studies of couples with cancer. We will also ask one global appraisal measure of how well they think they are communicating. Shared activities at each time point will be measured using 2 items developed by this team and used in our previous research on couples with illness. Patients and spouses are asked to rate engagement in a) fun activities together and b) physical activity together on a 0-4 scale.

#### Measures Relevant to Aim 3 (Feasibility & Acceptability)

There will be several indicators of feasibility and acceptability including refusal rate, number of sessions attended, and amount of time spent in each session. Dyads who receive at least 5 of the 7 sessions will be considered completers. Measures will also assess satisfaction with the program (amount of relevant information provided, interpersonal qualities of the interventionist) and advantages and drawbacks (e.g., I learned a lot during these sessions, the program took more time than I wanted to spend). These measures will only be administered to the treatment group (see attachment). Additionally, in a series of closed and open ended questions TCU participants will be asked about length of sessions, time between sessions, # of sessions and preferred delivery modality and two open-ended questions regarding benefits and drawbacks of the program.

Study data will be collected using REDCap (housed at Boston College). Standard descriptive statistics of frequency, central tendency, and dispersion will be used to describe the sample. All analyses will be performed using SPSS v26 (Chicago, IL) and HLM v7 (Skokie, IL). Our analytical approach to our previous dyadic research has used multilevel modeling (MLM) to control for interdependencies of the dyadic data. MLM provides a powerful and flexible framework for analyzing change. MLM, used with clustered data (e.g., couple data), extends multiple regression to the case where the responses of the members of the dyad are viewed as units nested within dyad. An important feature of MLM is that it allows for differences in both the number and spacing of the waves of data collection across dyad and controls for the autocorrelation among repeated assessment and nonindependent dyadic data. The dyadic model can be parameterized in two ways: 1) to examine a matched pairs model that explicitly allows for examination of actor, partner and within-dyad effects (i.e. APIM models) and 2) to examine dyadic appraisal or incongruence (gap between patient and care partner). Although these models are mathematically similar, the difference in parameterization allows for complementary information about the dyad to be modeled. These models have been described and used extensively by this team, including samples similar in size to the proposed study. Missing Data: We will examine attrition and patterns of missing data. In the case of data missing MCAR or MAR, model-based full maximum likelihood estimation will allow unbiased parameter estimation using all available data. Covariate Selection: Covariates will be identified for inclusion based on correlations with each outcome.

Aim 1: To determine the efficacy of the *Taking Care of Us* intervention on dyadic and individual health.

*Hypothesis: HF care dyads in the Taking Care of Us group will have better dyadic (i.e., better health (primary outcome), lower depressive symptoms and anxiety, better dyadic health and less healthcare utilization) and*

*individual health (i.e., lower care-related strain and better HF-specific QOL) compared with HF dyads in the control group.* Aim 2: To determine the efficacy of the *Taking Care of Us* intervention on dyadic appraisal & dyadic management. *Hypothesis: HF dyads in the Taking Care of Us group will have more similar appraisal of patient symptoms (i.e., dyspnea, pain, fatigue), greater collaboration in HF management behaviors and shared activities, and greater communication and dyadic confidence compared with HF dyads in the control group.* For Aims 1 & 2 we will have the following procedures. First, we will run a series of longitudinal APIM (matched pairs) models to simultaneously examine patient and care partner trajectories in health, depressive symptoms, anxiety, perceived dyadic health and healthcare utilization (Aim 1), engagement in heart failure behaviors, shared activities, communication and confidence (Aim 2) over time (controlling for interdependent data). Each HLM Level 1 model has four coefficients representing intercepts (baseline assessments) and slopes (rates of change) for patients and care partners that become outcome variables in an unconditional Level 2 model. Conditional Level 2 models will examine the effect of GROUP on patient and care partner dyadic health and dyadic management variables (controlling for covariates). A significant coefficient for GROUP on the slope parameter and a significantly better fitting model (as evidenced by the deviance statistic) will indicate the rate of change across time is statistically dependent on treatment condition. Second, to examine dyadic symptom appraisal, a longitudinal incongruence model will be used to directly examine patient-care partner dyadic appraisal over time where the slope represents the pattern of change in incongruence (gap in appraisal between the two members of the dyad). Three separate models will be estimated for each outcome (patient dyspnea, pain, & fatigue). We will know how large the gap is, the type of gap (e.g., care partner rating lower than patient), how the gap changes over time (e.g., increases, decreases, remains stable), and how much variability there is around the average pattern of change. The effect of TCU on dyadic appraisal will be tested directly by examining the role of GROUP. Third, for individual level variables (i.e., care strain and HF-QOL) individual MLM will be used to examine the role of GROUP.

Aim 3: To determine the feasibility and acceptability of the *Taking Care of Us* intervention. *We will determine feasibility and acceptability of the program to inform future studies.* Concurrent quantitative and two open-ended questions assessing satisfaction and advantages and drawbacks of the TCU program will be used to determine the acceptability of the program and any needed changes. Additionally, data regarding refusal rate, retention, and # sessions attended will be used to determine the feasibility of the program. Qualitative responses will be descriptively examined for value-added information to refine the program and understand quantitative responses. All data will be examined at the patient, care partner and dyad level to understand the strengths and limitations of the program within and across dyads.

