### **C. Materials, Methods and Analysis**

The proposed study is a two-group randomized controlled trial with separate assessments of patients and spouse care partners at 0, two months and five months. A community-based sample of patient-spouse care partner dyads will be recruited and randomly assigned by block (patient gender) to either the *Taking Care of Us* intervention or to an educational attention-control. All sessions will be delivered via Zoom (or phone) - there will be no in-person contact with participants throughout the study. *The term spouse refers to spouse or*

*unmarried partner.* All participants will be assessed three times baseline, two months and five months. We believe 7 biweekly sessions over two months, with the first follow-up interview taking place immediately at two months is realistic and appropriate. Our second follow-up will take place at five months to explore sustained effects. The attention-control group will receive three educational sessions over two months (at approximately 0-, 4- and 8 weeks). The sampling frame for the proposed research is community-dwelling adults with NYHA class II-III HF and their spouse/partner. The target sample is 72 couples with HF (36 couples per arm) with equal gender representation.

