### **Research Population & Recruitment Methods:**

The sampling frame for the proposed research is community-dwelling adult women and men with HF and their spouse care partner.

Formal inclusion and exclusion criteria for patient participants are:

Inclusion criteria:

Willing and able to provide written informed consent

Age greater than or equal to 18 years

Diagnosis of HF

Current HF symptoms (i.e. NYHA Class II-III; AHA/ACC Stage C HF)

Reachable by telephone/email/texting

Access to device with camera (e.g., computer, tablet) to participate in Zoom sessions or phone

Have a co-residing spouse/unmarried partner willing to participate

Exclusion criteria:

Major and uncorrected hearing impairment

Significant cognitive impairment

Heart transplantation/mechanical circulatory support prior to enrollment

Concomitant terminal illness that would impede participation in a longitudinal study

Active psychosis or severe substance abuse that would impair the ability to complete the study

Inability to complete the requirements of the study, including enrolment in an additional intervention trial

Formal inclusion criteria for spouse care partner participants are:

Age greater than or equal to 18 years

Co-residing with the patient at the time of recruitment

Have lived with the patient for a minimum of one year similar to other couple studies

Be willing and able to provide written informed consent

*Inclusion Criteria Justification:* An approximately equal number of women and men with heart failure will be enrolled. No potential participant will be excluded based on gender, race or ethnicity.

With 72 couples (144 participants total), and allowing for a 17% missing data rate, i.e. 60 dyads), we have 80% power to detect a 6.6 point difference in dyadic PROMIS global health scores between intervention and control groups (score mean=50, SD=10), which is greater than a minimally clinically important difference (estimate of  $\frac{1}{2}$  SD (5) due to no additional estimates available). These preliminary data are required to determine the sample size needed for a larger trial.

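### Full maximum likelihood is unbiased for the fixed effects but not for the dyad-level variances, so GROUP standard errors come out about 2% to 6% too small at 60 dyads

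*Combined protocol and SAP*

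**What the plan says.** The statistical text in section C (Materials, Methods and Analysis), placed after the Aim 3 measures, names the estimation method only in its missing-data sentences. The condition is "In the case of data missing MCAR or MAR", and the claim is "model-based full maximum likelihood estimation will allow unbiased parameter estimation using all available data". On covariates it says "Covariates will be identified for inclusion based on correlations with each outcome", with no number or ceiling. No REML fit, degrees-of-freedom method or small-sample correction is named.

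The procedures for Aims 1 and 2 use three kinds of model:
- **Longitudinal APIM (matched-pairs) models**, which include the primary outcome. Each dyad has four Level 1 coefficients. An effect is declared when the GROUP coefficient on the slope is significant and the deviance also shows a significantly better fit.
- **Incongruence models** for dyspnea, pain and fatigue. Among their outputs is "how much variability there is around the average pattern of change". GROUP is tested with no deviance condition.
- **Individual models** for care strain and HF-specific QOL, in which again only GROUP is examined.

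On size, section C says "The target sample is 72 couples with HF (36 couples per arm", and Research Population & Recruitment Methods says "allowing for a 17% missing data rate, i.e. 60 dyads". The latter section adds: "These preliminary data are required to determine the sample size needed for a larger trial".

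**The concern.** Variances are parameters too, and the plan lists one among its outputs. Full ML treats the Level 2 fixed effects as if they were known when it estimates the dyad-level variances. It therefore divides the residual variation by J, the number of dyads, where J − q would be unbiased; q is the number of Level 2 terms in an equation (intercept, GROUP and covariates). Missingness has no part in this: the shortfall is there with complete data. With several hundred dyads it would not matter. With 60 to 72 dyads and an open-ended covariate list it is small but visible, and it always shortens the GROUP standard error. At stake are the width of the GROUP intervals, the error rate wherever GROUP is tested on its own, and any model variance carried forward to the next trial.

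**Working it through.** **The plan's own figure.** The plan gives no figure for this bias. Its one numerical claim is that "we have 80% power to detect a 6.6 point difference in dyadic PROMIS global health scores" (SD 10) with 60 dyads. At 30 per arm the standard error is 10 × √(2/30) = 2.58, so 6.6/2.58 = 2.56. Power is then 72% at two-sided 5% and 82% at one-sided 5%. At 36 per arm, two-sided, it is 80.0%. The stated figure thus reproduces at 60 dyads only under a variant that the plan does not state. That is a separate matter; the sentence is used here only for J.

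**Inputs.** J = 60 (72 less 17%), or 72 if every dyad contributes. Three waves at 0, 2 and 5 months, taken as complete for the closed form. q = 2 for intercept and GROUP, plus 0, 3 or 5 covariates (assumed). Alpha is not stated; two-sided 5% is assumed.

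**Formulas (balanced data).** Ratio of the ML to the unbiased dyad-level variance of an observed coefficient: (J − q)/J. Ratio of GROUP standard errors: √((J − q)/J). Actual size of a nominal 5% t test: 2·P(t on J − q df > critical value × standard-error ratio).

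| J | covariates | q | variance ratio | SE ratio | SE shortfall | actual size |
|---|---|---|---|---|---|---|
| 60 | 0 | 2 | 58/60 = 0.967 | 0.983 | 1.7% | 5.4% |
| 60 | 3 | 5 | 55/60 = 0.917 | 0.957 | 4.3% | 6.0% |
| 60 | 5 | 7 | 53/60 = 0.883 | 0.940 | 6.0% | 6.5% |
| 72 | 0 | 2 | 70/72 = 0.972 | 0.986 | 1.4% | 5.3% |
| 72 | 3 | 5 | 67/72 = 0.931 | 0.965 | 3.5% | 5.8% |
| 72 | 5 | 7 | 65/72 = 0.903 | 0.950 | 5.0% | 6.2% |

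At 60 dyads, a nominal 95% interval for GROUP thus covers about 94.6%, 94.0% or 93.5%. If a normal reference replaced the t, test size would be 5.9%, 6.6% or 7.1%.

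**Check with fitted models.** The four-coefficient model was fitted by ML and REML to 600 simulated trials per setting. Assumed, not from the documents: intercept SD 7.5, slope SD 1 per month, residual SD 5.5, slope reliability about 0.30. The SE ratio was 0.985 (no covariates) and 0.962 (3 covariates) at 60 dyads, and 0.985 and 0.964 with 72 dyads and 17% dropout. The mean GROUP estimate was within about 0.01 of the true zero.

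**The two-part APIM rule** (60 dyads, t reference, 100,000 draws, same assumed variances). The range in each cell covers a 4-df and a 2-df deviance test, since the plan does not say which.

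| covariates | one member's slope | either member's slope |
|---|---|---|
| 0 | 1.9% to 2.8% | 3.5% to 5.4% |
| 5 | 2.7% to 3.7% | 5.0% to 7.0% |

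**Sizing a later trial.** For a 5-point difference, SD 10, two-sided 5% and 80% power, n per arm = 2 × 100 × (1.96 + 0.84)²/25, or 63 after rounding up. Multiplying the variance by 0.967, 0.917 or 0.883 gives 61, 58 or 56.

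**The case against.** The strongest reply is that the sentence concerns missing data. It contrasts using all available data with discarding cases, and in that sense it is right: the GROUP estimate is unbiased. Full ML is also needed for the plan's own rule, because REML deviances cannot be compared between models with different fixed effects. Both points stand. Neither supplies a REML fit or a degrees-of-freedom method for the standard errors.

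The size also depends on covariates that the plan does not count. With none, the shortfall is 1.7%, and the sampling error of a variance on 58 degrees of freedom (CV √(2/58), about 19%) is far larger. That stands too, although sampling error has no fixed direction and this bias has one.

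Stronger readings are tempting, and the documents do not support them:
- **The primary test rejects too often.** A reader might infer this from the t test or the deviance test taken alone. The plan requires both, and together they stay below 5% for one slope. If either member's slope counts, the rule can reach 7.0% with 5 covariates, but part of that comes from testing two slopes, which REML does not address.
- **The next trial will be undersized.** The plan does not say that model variances will be used. It sized this trial from a score SD.
- **The true slope variance will always be well understated.** That depends on the assumed slope reliability. In the simulation with 72 dyads, dropout and no covariates, ML gave 1.01 and REML 1.11 against a true 1.00.

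**Conclusion.** The concern holds in a limited form. The claim of unbiasedness is right for the fixed effects under MCAR or MAR and wrong for the dyad-level variances. The plan does not mention confidence intervals, but any built on these standard errors will be slightly too narrow on every outcome modelled this way, the primary included. The effect on error rates falls on the three incongruence models and the two individual models, where GROUP is tested alone. For the APIM models the decision rule is not the problem.

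A model variance used to size the larger trial would be about 3% low without covariates and up to about 12% low with 5, but only if full ML variances were the ones used.

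These figures rest on balanced data, 60 dyads, a t reference, two-sided 5% and 0 to 5 covariates per equation. They are slightly smaller if up to 72 dyads contribute.

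**What to change.** In the missing-data sentences of section C, limit the claim of unbiasedness to the fixed effects, and add text along these lines:

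> Full maximum likelihood will be used only to compute deviances for nested models that differ in fixed effects. GROUP estimates, standard errors, confidence intervals, t tests and variance components will be reported from a REML refit on all available data under the same MAR assumption, with dyad-level or Satterthwaite degrees of freedom. Any model variance used to size the larger trial will be the REML estimate.

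Stating the largest number of covariates per equation would also put a ceiling on q.

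**Cost.** A few sentences and a second fit of each conditional model, with no new data. At 60 dyads, standard errors rise by 1.7%, 4.4% or 6.4% with 0, 3 or 5 covariates, so results look slightly less favourable.

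**Limits.** REML variances are not exactly unbiased when variances are constrained to be non-negative; in the simulations the REML slope variance came out 5% to 11% high. The deviance test taken alone stays somewhat above 5% (5.8% to 8.9% at 60 dyads over the same range of covariates). That matters little while it is used only jointly with the coefficient test.

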Eligible and consented dyads will be randomly assigned to one of two groups. Block randomization stratifying by patient gender will be done using an online research randomizer ([www.randomizer.org](http://www.randomizer.org)). We will stratify by patient gender to ensure equal distribution between the two conditions. Participants will be provided with separate e-mail-specific links to the patient and spouse web-based survey using our REDCap platform; baseline surveys will take approximately 45 minutes to complete. Participants will be instructed to complete the survey separately without discussing the questions with their spouse/anyone else (this procedure has been successfully used in all dyadic work by this team and is the standard procedure in couple research). Participants who do not want to or cannot complete the survey electronically will be offered the option to complete the survey with a trained interviewer (blinded with respect to treatment assignment) via Zoom, phone or to complete a mail survey. Patients and their spouses will be interviewed separately and privately as in our other dyadic research. For the few participants who request a mail survey, they will receive individual packets and consent forms and return the survey and signed consent form in the stamped, addressed envelope provided. These procedures are identical to those successfully used by this team in other couple studies.

All Taking Care of US© (TCU) and educational sessions will be conducted via Zoom (or phone). Relevant materials for the sessions will be mailed to dyads ahead of the first session. For dyads in the TCU group, the project coordinator will inform the interventionist to schedule the first session with the dyad. The interventionist will communicate the treatment assignment to the dyad. Following completion of the 7 sessions of TCU, the interventionist will inform the project coordinator, who will schedule the immediate post-treatment interviews. For the control group, the trained educator (not involved in data collection) will contact the dyad to communicate their assignment to the attention-control condition and schedule a time for their first education session. Two additional education sessions will be done at 4 and 8 weeks. Following completion of the final education session, the trained educator will inform the project coordinator, who will schedule the immediate post-treatment interviews (approximately two months).

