HF patients are generally older, though it can occur at any age. Those younger than 18 will not be approached for enrollment as the underlying heart failure pathology (e.g. congenital heart defects) is dissimilar to those with coronary artery disease, hypertensive heart failure and other forms of cardiomyopathy and our focus on couples renders the study not relevant to children. Based on epidemiologic data, we anticipate an age range of 18 to 90 with an average of approximately 60-70 years. Our previous HF patient samples have had means of approximately 57 years of age. We anticipate that spouses/unmarried partners will have a similar age distribution. HF occurs in both genders and in persons of all races and ethnicities. No potential participant will be excluded based on gender, race, ethnicity, or sexuality. As an equal number of men and women comprise the HF patient population, approximately equal numbers of men and women will be enrolled in the proposed study (along with their spouse/partner). Specifically, we plan to stratify our randomization by patient gender to ensure equal representation of patient gender across our intervention and attention-control conditions. As with our previous HF research, if enrollment in the total sample becomes imbalanced, every effort will be made to increase the enrollment of the underrepresented gender.

Robust enrollment and retention of persons from minority populations is absolutely desired in the proposed study to achieve our goal of a representative sample of patients with HF (and their care partners). Planned enrollment is based on the distribution of race in Massachusetts where the sample will be drawn. Most recent data shows 80.8% of people in Massachusetts are Caucasian (71.4% Caucasian non-Hispanic or Latino), 8.9% are African American, 7.1% are Asian, 0.5% are American Indian/Alaska Native, 0.1% are Native Hawaiian/Other Pacific Islander, 2.5% report two or more races and 12.3% are Hispanic or Latino.

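### Covariates are to be chosen outcome by outcome from correlations, and patient gender, the randomization stratum, is not assured a place in any model

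*Combined protocol and SAP*

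**What the plan says.** The analysis text in section C (it follows the Aim 3 measures) states the selection rule once: "Covariates will be identified for inclusion based on correlations with each outcome". No covariate is named there or anywhere else in the document.

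For the matched-pairs models of Aims 1 and 2, the Level 1 model has "four coefficients representing intercepts (baseline assessments) and slopes (rates of change) for patients and care partners that become outcome variables". The next step is then described: "Conditional Level 2 models will examine the effect of GROUP on patient and care partner dyadic health and dyadic management variables (controlling for covariates"). A treatment effect is declared from GROUP on the slope together with improved model fit. For the incongruence models (dyspnea, pain, fatigue) and the individual-level models (care strain, HF-specific quality of life), the text names GROUP only and mentions no covariates.

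The design side is explicit. Section C says "Block randomization stratifying by patient gender will be done using an online research randomizer", and the recruitment section repeats "we plan to stratify our randomization by patient gender".

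**The concern.** Two things do not fit together. First, the adjusted model is not fixed for any outcome. The rule works separately for each outcome and has no cut-off, so two analysts following the text could adjust the primary outcome for different variables. Second, the trial randomizes within patient gender, but gender enters a model only if it happens to correlate with that outcome. Some outcomes could be analysed with the stratum and others without it.

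What is at stake is a match between design and analysis, a small amount of precision, and an analyst's choice that need not exist. Although this is a pilot, the aims are worded as determining efficacy, effects are judged by significance, and the results are meant to inform the size of a larger trial.

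**Working it through.** **No figure of the plan's own is at issue.** The document gives no number for covariate adjustment. Its one power statement (80% for 6.6 points, 60 dyads, SD 10) names no covariates, and this point does not rest on it.

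**1. How often could gender be left out?** Inputs from the document: 60 analysable dyads, with about equal numbers of women and men as patients. Assumed: a two-sided correlation screen, one outcome per model, and the share R² of outcome variance that gender explains. The screen is a t test on 58 degrees of freedom with noncentrality √(60·R²/(1−R²)). At R² = 5% this is √(3/0.95) = 1.78, against a critical value of 2.00 for p<0.05. Gender is then included with probability 0.416 and omitted with probability 0.584.

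| Assumed R² | Omitted, p<0.05 screen | Omitted, p<0.20 screen |
|---|---|---|
| 1% | 88% | 67% |
| 2% | 81% | 56% |
| 5% | 58% | 31% |
| 10% | 28% | 10% |

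The matched-pairs models hold two outcomes, patient and care partner. If gender could be flagged through either member (same gender effect on both, within-dyad correlation 0.3 to 0.5, p<0.05), simulated omission falls to about 79–80%, 68–70%, 39–42% and 11–14% in the same four rows. These figures describe inconsistency, not error, and they move with every assumption.

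**2. What does omission cost the planned slope test?** Take one dyadic score per dyad, complete visits at 0, 2 and 5 months, 30 dyads per arm, random slopes uncorrelated with intercepts, and GROUP on intercept and slope. The variance of the slope contrast is

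(2/30)·(τ² + σ²/S),

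where τ² is the slope variance, σ² the residual variance and S = (0+4+25) − 7²/3 = 12.67. The intercept variance does not appear. So if gender predicts only the level of the score, adding it changes the slope standard error by 0%.

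If gender also explains part of τ², there is a small effect. The variance components are assumed:
- Smallest of four cases (σ²=40, τ²=1, gender explains 5%): √[(0.95+3.158)/(1+3.158)] = 0.994, a cut of 0.6%.
- Largest (σ²=20, τ²=4, gender explains 10%): √[(3.6+1.579)/(4+1.579)] = 0.963, a cut of 3.7%. It is 3.9% if GROUP is on the slope only.

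The range is therefore 0 to about 4%.

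**3. Which way does the error go?** In a simplified single-endpoint analysis, allocation balanced on gender makes the true standard error √(1−R²) times the one an unadjusted analysis reports. The rejection rate under no effect is then about 2·[1−Φ(1.96/√(1−R²))]: 4.4%, 3.9% and 2.8% at R² of 5%, 10% and 20%. Simulation gave 4.5%, 3.7% and 2.9%, against about 5% with gender in the model. Omission makes the test conservative.

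**4. Does the selection rule itself inflate error?** A single-endpoint simulation used 60 dyads, gender plus 8 candidate covariates, and a p<0.05 screen. Applied mechanically, the rule gave type I error of 4.6–5.5%. Taking the smallest p-value from the unadjusted, gender-adjusted and screened models gave 6.3–7.1%. The second range shows what an open choice permits; nothing in the document proposes it.

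**The case against.** The strongest reply is that nothing of inferential weight is lost. Stratified allocation is there to balance gender, so leaving it out is not confounding. The slope test barely moves, the rule applied mechanically holds its error rate, and the trial is a pilot. All of that stands, and it limits the point to a modest one.

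Four stronger readings are tempting, and the documents do not support them:
- *The rule inflates false positives or biases the effect.* Mechanical use gave about 5%, and omitting the stratum errs on the conservative side. The 6.3–7.1% needs an analyst who picks the best of three models.
- *Gender will usually be missing from the primary model.* The document gives neither a threshold nor a gender effect, and a range of 10% to 88% predicts nothing.
- *Covariates will certainly be chosen after outcomes are seen.* That is the natural reading, but the sentence does not say which data or which visit. The firm statement is that the rule is unspecified.
- *Every model must share one covariate set.* Different prognostic covariates for different outcomes are legitimate if listed in advance.

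What the reply does not answer is that the text, as written, admits the stratum only by chance correlation and leaves the adjusted model open for every outcome.

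**Conclusion.** The point holds in a limited form. The document names patient gender as the stratum in more than one place and names no covariate in any model; its only rule lets the stratum in or out according to observed correlation. The consequence is a possible mismatch between design and analysis, standard errors too large by 0 to about 4% for the slope test, and an avoidable analyst's choice.

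The 4% rests on assumed variance components and on gender explaining 5–10% of intercept and slope variance. The direction, conservative rather than inflated, rests on allocation being balanced within gender. The omission percentages are illustrative only. The change is worth making because it costs almost nothing, not because the planned tests would be invalid without it.

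**What to change.** Replace the correlation rule with covariates fixed before any outcome data are examined, either as one common set or as a listed set for each outcome. Always include patient gender:
- in the Level 2 intercept and slope equations of the matched-pairs models, for both patients and care partners;
- in the incongruence models and the individual-level models, where the text now names only GROUP.

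Report models with correlation-selected covariates as sensitivity analyses only, with the candidate list and cut-off stated.

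The cost is one or two sentences in the analysis text. Gender is already known at randomization, so no new data are needed. The price is about one parameter per equation, hence four in a matched-pairs model with its two intercepts and two slopes. With about 60 dyads that is affordable, and it is a reason to keep the rest of the list short.
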